 - The volunteer will join the meeting at the scheduled time.
 - The UMass RA will explain about the assessment.
 - Message:
 - Group A: "*OK. I will give the overall process of our study first. Our study participants are divided randomly into Group A/B. You are selected as Group A. It means that for the first 12 weeks, you play a cognitive game with the provided tablet PC. We will also follow up on your game playing experience and your cognitive and physical activity by call and email survey. They will be very brief and take about 1 min. After 12 weeks, you need to return a table PC, and do the second assessment, and don't need to do anything particular for the next 12 weeks. We will just check your cognitive and physical activity. For this assessment, an important note is that [Rutgers RA] should not know about which group you are in. Please know that [Rutgers RA] is only here for the assessment purpose. To assess your cognitive function without any bias, [Rutgers RA] should not know which group you are in, you already received a table PC, and start to play a game soon. So, if you have any concerns or questions related to our overall study procedure, game play or tablet PC, please feel free to talk to me or ask me. {optional} For today's assessment, [Helper Name] will be asked survey questions related to [participant name]'s daily activity first before starting cognitive assessment. I will break a zoom room for [participant name] during the survey, and let [participant name] join again after completing the survey. [participant name], do you feel comfortable with using zoom? After completing the survey, [helper name] please stay in the house but not in the room during the assessments.} The entire assessment will be video-recorded for future reference. Now the [Rutgers RA] will join and start the assessment. I will stay muted until the assessment is over, but if you have a question, please feel free to ask me.*

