- Group B: “OK. I will give the overall process of our study first. Our study participants are divided randomly into Group A/B. You are selected as Group B. It means that For the first 12 weeks, you don’t need to do anything for this study but we will just check you about your cognitive and physical activity such as puzzles, board games or hiking like that. After 12 weeks, you will receive a table PC and play a cognitive training game. For this assessment, an important note is that [name] should not know about which group you are in. *Please know that [name3] is only here for the assessment purpose. To assess your cognitive function without any bias, [Rutgers RA] should not know that you are starting 12 weeks with no game play and you will receive a table PC 12 weeks later. So, if you have any concerns or questions related to our overall study procedure, game play or tablet PC, please feel free to talk to me or ask me. {(optional) For today's assessment, [Helper Name] will be asked survey questions related to [participant name]'s daily activity first before starting cognitive assessment. I will break a zoom room for [participant name] during the survey, and let [participant name] join again after completing the survey. [participant name], do you feel comfortable with using zoom? After completing the survey, [helper name] please stay in the house but not in the room during the assessments.} The entire assessment will be video-recorded for future reference. Now the [Rutgers RA] will join and start the assessment. I will stay muted until the assessment is over; but if you have a question, please feel free ask to me.”*”
-
- The UMass RA will bring the Rutgers RA back to the main meeting room and start **recording the assessment**.
- Five different **Assessment Form (1-5) instruments** have a different randomized order of tests. RAs select an assessment form using **Assessment/Assessment Form Assignment.xlsx** in Google drive. Then, the questions and fields of the selected **Assessment Form instrument** will appear.
- The Rutgers RA will administer all the assessments and enter all answers to **the corresponding Assessment Form instrument**. The Rutgers RA will score the participant as he/she administers the assessments.

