 - Message: *“Do you have any questions so far? If not, I would like to explain what will happen next. We will ask you to play Neuro-World for 30 minutes a day, 2 days a week for 12 weeks. (accurate exactly two days, separate day) We already installed the cognitive training program, Neuro-World, in the table computer we sent. Also, we will call you twice a week to follow up your training. The call will take 1-2 minutes to briefly follow up on your training and thoughts related to the training. Before you start the training with the Neuro-World game, We will need to schedule a training session where we will go over all the games together and help you learn how to play all those games. It will take about one hour to go over all the games. When would be available to you this week or next week? ”*
 - Group B: *“Do you have any questions so far? If not, I will start to check your physical and cognitive activity about next week. I will send surveys to you very simple questions three times a week and call you twice a week. The phone call will take about 2 minutes. 12 weeks from now, we will ask you to play the cognitive training game, Neuro-World. Until then, we will follow up with you twice a week.”*

- All participants will be assessed using the following tests.

- We will use the original assessment if it is a questionnaire that can easily be done online.
- We will use the modified version for the videoconference-based administration (as opposed to telephone-based), if the original assessment is difficult to be done online. (According to [name]) Some assessment tools, such as MoCA and MMSE, also test the visuospatial function of participants. The participants' performance on visuospatial-related questions is important information as well, which makes the videoconference-based version superior to the telephone-based version.

- The convention for naming the video-recorded interactions. **P1_A1_20210623.mp4** (participant number, event type and number, date)

- Assessments (before, after, follow-up) [A1, A2, A3]
- Weekly check-ups [C1, C2, ...]
- participants' initiated questions [Q1, Q2, ...]
- Online workshops [W]

- The computer that the researchers initially record audios/videos need to be encrypted (e.g., Windows 10 BitLocker Drive Encryption) and password-protected.

6. Shipping tablet PC (UMass RA will perform)

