 - In the past two days, did you do any PHYSICAL activities or exercise such as going for a walk, biking, swimming, exercise videos/classes or anything else you can think of?
 - If yes, how long?
- For the caregiver (optional),
 - During this week, did you meet the participant?
 - In the past two days, did you see the participant do any COGNITIVE activities such as Sudoku, board games, word games, or any other activities you do to help your memory and mental capacity?
 - If yes, how long?
 - In the past two days, did you see the participant do any PHYSICAL activities or exercise such as going for a walk, biking, swimming, exercise videos/classes or anything else you can think of?
 - If yes, how long?

9. Assessment after 12 weeks (Only Rutgers RA can perform assessment; UMass RAs will organize the overall meeting)

- After 12 weeks, all participants will be assessed with the following tests **online (via zoom)**.

Detailed steps will be the same as the baseline assessment.

RAs will generate a new form for recording 12 weeks follow-up assessment from the corresponding Assessment Form instrument.

10. Returning tablet PC (UMass RAs will perform)

- A UMass RA will track the returning delivery of the tablet computer.
 - The UMass RA should have instructed the participant or the caregiver to return the tablet computer. If not,
 - Call the participant or the caregiver to provide the instructions. (Refer to **8. Checking compliance every week**)
 - The UMass RA, who is on the designed days, will check the tracking number based on **the Tracking number field (Returning to the UMass from the subject) of the Tablet Ship & Return instrument**. The following is an example.
 - UMass RA1: Wed
 - UMass RA2: Fri
 - If the returning package has been picked up by the UPS,
 - Enter the date in **the Shipped date field of the Tablet Ship & Return instrument**.
 - If the returning package is shown delivered,
 - The RA will retrieve the tablet computer.
 - The RA will check if both the tablet computer and the charger are included in the box.
 - If the returning package is shown delivered but the package is not delivered,
 - The RA will contact the UPS and file a claim.

11. Interview (UMass RAs will perform)

- A UMass RA will remind the participant and the caregiver of the scheduled interview.
 - Give a call to the participant and the caregiver, remind them 1 day before the scheduled interview in the following order.
 - Phone call
 - If not answering, text and email.

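### Both pre-assessment scripts invite questions to the unblinded RA, with no private channel, while the blinded assessor is in the room scoring, and weeks 12 and 24 have no script of their own

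*Protocol*

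**What the plan says.** Protocol section 5 (Assessment at baseline) sets out a meeting in which a UMass RA, who knows the allocation, hosts, and the Rutgers RA, who does not, assesses. The Rutgers RA waits in a breakout room while the UMass RA reads a group-specific script.

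Both scripts say that the assessor should not know the group, and both direct sensitive topics to the UMass RA: "if you have any concerns or questions related to our overall study procedure, game play or tablet PC, please feel free to talk to me". The Group A script ends with "I will stay muted until the assessment is over, but if you have a question, please feel free to ask me" and the Group B script with "I will stay muted until the assessment is over; but if you have a question, please feel free ask to me".

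The next step reads "The UMass RA will bring the Rutgers RA back to the main meeting room and start" the recording. On scoring, the section says "The Rutgers RA will score the participant as he/she administers the assessments".

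Sections 9 and 12, for weeks 12 and 24, contain no script. Each says "Detailed steps will be the same as the baseline assessment". The role table at the front of the protocol nevertheless gives the UMass RA general instructions to deliver before the assessment at both follow-up visits.

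**The concern.** The topics that the participant is told to raise with the UMass RA (study procedure, the game, the tablet) are the ones that reveal allocation. The closing sentence then allows questions during the session, when the assessor can hear them. Participants have cognitive impairment and the session lasts about two hours, so a single warning at the start is a thin barrier.

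The exposure grows at follow-up. By week 12 a participant has either trained for 12 weeks or not, and has something concrete to mention. With only two sequences, a disclosure at week 12 also tells the assessor the sequence for week 24. Only the Rutgers RA may assess at any visit, and the text available names no back-up rater. If the assessor, once aware, scored even slightly in favour of training, the shift would be in the direction that the SAP's one-sided test is looking for, and a larger sample would not reduce it.

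**Working it through.** The plan states no figure on this point, so there is none to reproduce. The check is to follow the session in order and then ask what carries over to follow-up.

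**The session as written (Protocol section 5)**

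1. The assessor is in a breakout room while the script is read. Blinding is protected.
2. The script warns that the assessor must not know the group, and routes revealing topics to the UMass RA. This also protects the blind.
3. The script ends by inviting questions during the assessment. It does not exclude the topics in step 2 and names no chat, breakout room or deferral.
4. The assessor is brought into the main room and scores live. Under step 3, a question about the game or tablet would be put in the assessor's hearing.
5. At the end the assessor texts the UMass RA, the UMass RA unmutes, and the assessor leaves, in that order. This is a second, shorter window for the same leak.
6. The next-step message for each group comes after the assessor has left.

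The gap is therefore in steps 3 to 5.

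**What carries over to weeks 12 and 24**

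- The general rule (the assessor should not know the group) is correct at every visit.
- The examples attached to it are not. Group A is told that the assessor "should not know which group you are in, you already received a table PC, and start to play a game soon". Group B is told to conceal that a first period without games is about to begin. At follow-up, what needs concealing is the training or control period just completed, and the tablet.
- No other text in sections 9 or 12 supplies this.

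**How a scoring drift would enter the analysis**

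Read SAP section 2 as comparing change over the intervention period with change over the non-intervention period, with W0, W12 and W24 the scores at the three visits:

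- Group A: D = (W12 − W0) − (W24 − W12) = 2·W12 − W0 − W24
- Group B: D = (W24 − W12) − (W12 − W0) = W24 + W0 − 2·W12

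Week 12 carries weight 2; baseline and week 24 carry weight 1 each. A drift of b points at the end-of-training visit adds 2b to D in Group A and b in Group B. With equal groups the mean is (2b + b)/2 = 1.5b. If a share f of participants is affected, the mean shift is 1.5·b·f.

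To see whether this can be turned into a size, assume b = 0.5 to 1 point, a standard deviation of D of 2 to 4 points, equal groups and all 50 participants analysed. None of b, f or the standard deviation is in the documents. The noncentrality is 1.5·b·f·√50/SD, with 49 degrees of freedom and one-sided 0.05 (critical t 1.677).

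- f = 10%: lowest case 0.075 × 7.071/4 = 0.133, type I error 0.065; highest case 0.15 × 7.071/2 = 0.530, type I error 0.131.
- f = 25%: 0.094 to 0.368.
- f = 50%: 0.161 to 0.834.

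The result runs from almost nothing to a worthless test, depending wholly on assumed inputs. That is why no size is claimed.

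**The case against.** The strongest reply is that the protocol plainly intends blinding and protects it in several ways. The assessor is kept out while the script is read, the participant is told why the assessor must not know, revealing questions are steered away from the assessor, and the randomization list and form are hidden from Rutgers staff. Sessions are also recorded, so doubtful scores could be looked at again. All of this stands. It lowers the risk, but none of it makes the question route private while scoring is under way.

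Several stronger readings are tempting, and the documents do not support them:

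- A reader might infer that the baseline scripts are read word for word at weeks 12 and 24, so that the confidentiality instruction there is wrong. The text says that the detailed steps are the same; verbatim reuse is an inference. The general rule stays valid and only the examples date.
- A reader might infer that the Group B closing message, "12 weeks from now, we will ask you to play the cognitive training game, Neuro-World", endangers the blind if repeated at week 12. It could not, because it is spoken after the assessor has left. Repeated literally at week 12, it would conflict with the sequence in section 4, but that is a separate tidying matter.
- A reader might put one bias in points on every scale. The scales have different ranges. GDS and SF-36 are questionnaires, which leave less room for rater judgement than MoCA, MMSE or digit span.

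It is also fair to say that moving the assessor out mid-session interrupts standardised testing, and that asking the only assessor at each visit to guess the group could itself prompt guessing before later visits. The fix below takes account of both.

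**Conclusion.** The point holds as a gap in procedure. Followed as written, the scripts permit allocation-revealing questions in the hearing of the only blinded assessor during live scoring, and the follow-up visits lack wording that names what must then be concealed. A reader might go further and infer that the assessor will be, or has been, unblinded, or that the results will be biased by a given amount. The documents show neither, and give no unblinding rate, rater drift or outcome variability from which to estimate one.

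The conclusion rests on two readings: that a question to the UMass RA would be spoken in the shared room, since no other channel is named, and that no visit-specific script exists outside the text available. It is a cheap improvement that should be made. It does not show that the design fails.

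**What to change.** 1. In both scripts, replace the closing invitation with wording such as: *Please keep any question about the study, the game or the tablet until the assessor has left. If you cannot wait, say only that you need a break.* The UMass RA then moves the assessor to the breakout room already in use before any talk. At the end, the assessor leaves before the UMass RA unmutes.
2. Add short scripts to sections 9 and 12 asking participant and helper not to mention games, the tablet, training or what comes next. Separately, as tidying, make the next-step message for each group at each visit agree with the sequence in section 4.
3. Add one REDCap field in which the assessor records any actual disclosure of allocation when it occurs. Do not ask for a guess at each visit.

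The cost is script edits and one data field, with no new staff or visits. The downside is an occasional brief pause in testing.

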Official Study Title:

Towards the development of a mobile-health technology designed to encourage the use of serious game-based interventions in patients with mild cognitive impairment outside the clinic

NCT Number:

NCT04920123

Document Type:

Study Protocol

Document Date:

February 05, 2025

STUDY PROTOCOL

Study Procedures:

1. [Recruitment](#)
2. [Screening](#)
3. [Informed consent obtainment](#)
4. [Random assignment into two groups](#)
5. [Assessment at baseline](#)
6. [Shipping tablet PC5. Assessment at baseline \(Only Rutgers RA can perform assessment; UMass RAs will organize the overall meeting\)](#)
7. [Tutorial for the intervention group](#)
8. [Checking compliance every week \(twice per week\)](#)
9. [Assessment after 12 weeks](#)
10. Returning tablet PC
11. Focus group (Online workshop)
12. Assessment after 24 weeks

Role Assignment

	UMass RA	Rutgers RA
Recruitment	O	O
Screening	O	O
Informed consent obtainment	O	O
Random assignment into two groups	O	X
Assessment at baseline	O (general instructions before assessment)	O (actual assessment)
Shipping tablet PC	O	X
Tutorial for the intervention group	O	X
Checking compliance every week	O	X
Assessment after 12 weeks	O (general instructions before assessment)	O (actual assessment)
Returning table PC	O	X
Focus group (Online workshop)	O	X
Assessment after 24 weeks	O (general instructions before assessment)	O (actual assessment)

1. Recruitment:

- **50** participants with Mild Cognitive Impairment (MCI) will be recruited as follows.

[figure not shown]
- Currently planned means:
 - Emailing recruitment flyers to residents in local senior centers in Amherst, MA and Union, NJ
 - Emailing recruitment flyers to support groups and conferences
 - Posting recruitment flyers on the Internet (e.g., ClinicalTrials.gov, National Alliance on Mental Illness; nami.org, Alzheimer's Association; alz.org, UMass newsletter)
 - Posting an abbreviated recruiting message + screen shots of flyers on the social media (e.g., Facebook, Twitter)
 - Recruiting message: *"If you believe you have mild cognitive impairment, and are interested in cognitive training using mobile games, please contact AHHA Lab [contact], [contact].)"*
 - Visit senior villages
- Optional means:
 - Using paid third-party services that perform the recruiting process
 - Advertising on local newspapers

- The flyer can be found in [**Appendix 1**](#). (unified phone number / email address)

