- The researcher (i.e., a UMass RA) will contact the participant or the caregiver separately to ask about any potential issues.
- Should they have any questions, the participant or the caregiver can contact the UMass RA anytime through a phone call or an email to schedule a meeting. → Zoom link will be sent at a scheduled time. Video-record interactions.

- The UMass RA will store the video-recording in the MS OneDrive

- The UMass RA will initially store the Zoom video-recording in the encrypted & password-protected local computer.
- The UMass RA will upload the file to the HIPAA-compliant cloud storage supported by UMass Amherst (MS OneDrive)
- The UMass RA will remove the file from the local computer.

8. Checking compliance every week (UMass RA will perform)

- UMass RAs will follow up with the participant twice a week for 24 weeks by phone call.
- If the caregiver participates in the study, UMass RAs will follow up with the caregiver once a week for 24 weeks by phone call.

- The phone follow-up will be audio-recorded.
- For the participant,
 - During the experiment period
 - When the participant successfully adheres to Neuro-World training, a casual follow-up.
 - Message: "*How is Neuro-World training going?* Are there any significant changes in your daily activities? Could you explain in more detail? Thank you."
 - When the participant missed Neuro-World training this week, try to understand what hinders the participant's low adherence.
 - Message: "I noticed that you have not played Neuro-World this week. Is everything ok? Do you need any help?"
 - At the last follow-up call, ask the participant to return the tablet computer & arrange the 1:1 interview.
 - Message: "So, this week is your last Neuro-World training. Would you be able to return the tablet computer? Please wrap the tablet computer using bubble wrap. Put the wrapped tablet computer and the charger in the air-inflated package. Put the package in the paper box. Put the returning label on the box."
 - The RA will schedule the earliest available time for the participant and both UMass RAs.
(AHHA lab account, [contact])
 - For more details about the interview, refer to **11. Interview**.
 - During the control period
 - Message: (for MCI participant) "Are there any significant changes in your daily activities? Could you explain in more detail? Thank you."

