 - Give a call to the participant and the caregiver, remind them 2 hours before the scheduled interview.
 - Phone call
 - If not answering, text and email.
- Both UMass RAs and PIs (if applicable) will attend the interview.
 - One UMass RA will initiate a zoom meeting.
 - The UMass RA will email a zoom link to the participant (or the caregiver), another UMass RA, and PIs approximately 10 minutes before the scheduled time.
- List of potential questions for the participant.
 - What information and how do participants want to receive to better comprehend their cognitive performance and their compliance behaviors (frequency and duration)?
 - Can you tell us which Neuro-World games you did well?
 - How well did you do those games?
 - Can you tell us which Neuro-World games you did poorly?
 - How poorly did you do those games?
 - Is there anything else you want to know about your performance while you were playing those games?
 - Did you enjoy playing Neuro-World games?
 - What did you enjoy about playing Neuro-World games?
 - What did you not enjoy about playing Neuro-World games?
 - Can you tell us if knowing your performance in Neuro-World games helped you play Neuro-World routinely?
 - What other information would help you adhere to playing Neuro-World routinely?
 - What is the optimal design of the feedback mechanism (content, medium, and timing) to remind participants to self-administer the training?
 - What made it easy to access the information about your performance in playing Neuro-World games?
 - What made it difficult to access the information about your performance in playing Neuro-World games?
 - How can we present the information so that you can access it more easily?
 - What made it easy to understand the information about your performance?
 - What made it difficult to understand the information about your performance?
 - How can we present the information so that you can understand more easily?
 - How many times or often did you access the information about your performance?
 - How often would you be willing to access the information if it were presented in a way you preferred?
 - Are there any interaction barriers, such as video/audio instructions that may not be sufficiently informative, for participants to use the system, which have not been observed in our preliminary studies?
 - What made it easy to play Neuro-World?

- What made it difficult to play Neuro-World?
- Did you find the Tutorial easy to understand?

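### Nothing requires the end-of-training interview to wait for the end-of-training assessment, so a game debrief with unblinded staff may come immediately before those outcomes but never immediately before end-of-control outcomes

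*Protocol*

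**What the plan says.** Protocol section 8 (Checking compliance every week) sets the booking step for the training period: "At the last follow-up call, ask the participant to return the tablet computer & arrange the 1:1 interview". The script for that call begins "So, this week is your last Neuro-World training", so the booking is made in the final training week. The timing rule is "The RA will schedule the earliest available time for the participant and both UMass RAs". The helper's entry in the same section has the same rule.

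The step list gives the week-12 assessment as step 9 ("After 12 weeks, all participants will be assessed with the following tests"), then "11. Interview (UMass RAs will perform", then "12. Assessment after 24 weeks". The opening list of procedures names step 11 differently: "11. Focus group (Online workshop".

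The question list in section 11 covers performance and enjoyment, for example "Can you tell us which Neuro-World games you did poorly". Both UMass RAs attend, and the PIs where applicable. Under section 4 the UMass RAs hold the allocation file, and the randomization form is hidden from Rutgers personnel, who rate the outcomes.

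The control-period script in section 8 arranges no interview.

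**The concern.** A crossover comparison assumes that the training and control assessments are taken under the same conditions apart from the training itself. A structured conversation about how well the participant played, and whether they liked it, is a different condition if it comes shortly before one of those assessments and has no counterpart before the other.

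Three kinds of outcome data are exposed.

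- **Self-report.** GDS and the SF-36 mental component are the participant's own answers. A blinded rater does not protect them from a change in mood or expectation.
- **Rater-administered tests.** Section 5 scripts a warning that the Rutgers RA must not learn the group. A recent debrief about the games makes an accidental remark more likely.
- **Helper report.** Where a helper is enrolled, section 5 has the helper answer questions about the participant's daily activity at the assessment session. The helper's interview therefore raises the same question.

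SAP section 2 specifies paired t-tests of intervention against non-intervention periods and names no sequence or period term. Any shift confined to the end-of-training visit would be counted as treatment effect.

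**Working it through.** The plan gives no figure on this point. The check is mainly of the timetable, followed by an illustration on assumed inputs.

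**1. Which visit ends which period (section 4).** Group A trains in weeks 1–12, so week 12 ends training and week 24 ends control. Group B trains in weeks 13–24, so week 12 ends control and week 24 ends training.

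**2. Where the interview can fall.**

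| | End-of-training visit | Step list, read literally | Booking rule in section 8 |
|---|---|---|---|
| Group A | Week 12 (step 9) | Assessment, then interview | Either order permitted |
| Group B | Week 24 (step 12) | Interview, then assessment | Either order permitted |

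**3. Is the step list a timeline?** Not for Group B. It places tablet shipping (step 6) and the tutorial (step 7) before the week-12 assessment (step 9), yet the Group B briefing in section 5 says the tablet comes after 12 weeks. Step 8 runs for all 24 weeks, across steps 9 to 12. The list fits Group A's path and leaves Group B's order open. The recruitment flyer says only that the online session follows the 24 training sessions, which does not settle it.

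**4. Before end-of-control visits.** Group B has had no interview by week 12. Group A has had one, about 12 weeks before week 24. So an interview never comes immediately before an end-of-control assessment.

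**5. Illustration only.** Inputs from the documents: n = 50 (Protocol section 1) and one-sided alpha 0.05 (SAP section 2). Everything else is assumed: a shift of d points at week 24 in Group B only, equal group sizes, visit-level SD 1.5 to 2 with independent visits, no dropout, and *changes* in the SAP read as within-period change scores.

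- Group A contrast: (w12 − w0) − (w24 − w12) = 2·w12 − w0 − w24.
- Group B contrast: (w24 − w12) − (w12 − w0) = w24 − 2·w12 + w0.
- A shift d at week 24 moves each Group B contrast by d, so the pooled mean moves by d/2.
- SD of the contrast = √(4+1+1) × SD = 2.449 × 1.5 = 3.67, or 2.449 × 2 = 4.90.
- Noncentrality = (d/2) × √50 / SD of contrast. For d = 0.5: 0.25 × 7.071 / 3.67 = 0.48, or 0.25 × 7.071 / 4.90 = 0.36.

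Rejection probability under a true null, from the noncentral t with 49 df and critical value 1.677:

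| Assumed d (points) | SD 1.5 | SD 2 |
|---|---|---|
| 0.5 | 12.1% | 9.9% |
| 0.2 | 7.3% | 6.6% |
| 0 | 5.0% | 5.0% |
| −0.2 | 3.3% | 3.7% |
| −0.5 | 1.7% | 2.3% |

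If the SAP instead means end-of-period scores, the contrast SD is √2 × SD = 2.12 to 2.83, and d = 0.5 gives about 15–21%. One value of d and one SD range stand in for scales as different as GDS and SF-36, so these figures show how the mechanism works and estimate nothing about this trial.

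**The case against.** The strongest reply is that the interview adds little. UMass RAs already ask about training twice a week up to the last training week. The week-12 and week-24 visits follow the baseline steps, in which an unblinded UMass RA talks to participants in both groups about group, game and tablet just before the rater joins. The participant has also only just finished playing. This stands as a limit on the claim: what the interview adds is unknown. It does not dispose of it. The training calls are described to Group A as lasting 1–2 minutes, whereas the interview is a long set of questions on performance and enjoyment with several staff present. Its direction is also open, since it asks about poor performance and difficulty as well as success.

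Four stronger readings are tempting, and the documents do not support them.

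- *Group B is always interviewed before its final assessment.* This takes the step numbers as Group B's schedule, which they cannot be.
- *Game performance is never discussed before an end-of-control assessment.* This is false for Group A, whose interview precedes its week-24 visit by about 12 weeks. Only *never immediately before* holds.
- *The interview slot will be found sooner than the assessment slot.* The interview needs both UMass RAs and possibly the PIs. The assessment needs one UMass RA and the Rutgers RA, and the two-hour block is stated for baseline.
- *Both groups are interviewed first, with a much larger error rate.* For Group A this contradicts the listed order. The booking rule permits it, but nothing shows that it is intended.

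**Conclusion.** The concern holds as a gap in the schedule. The protocol does not fix the order of interview and end-of-training assessment, and its only timing rule allows the interview first. The exposure, if it occurs, falls on the training side and may differ between sequences.

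No bias has been shown. The size and direction of any shift cannot be derived from the documents, which give no SD or effect size. The error rates above depend wholly on the assumed shift and SD, and they would stay at 5% if assessments already come first in practice. The change is worth making because the exposure is avoidable and the remedy is nearly free, not because a large effect is likely.

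**What to change.** In section 8, for the participant and helper entries alike, replace the present timing with: *earliest available time after that participant's end-of-training assessment is complete (week 12 for Group A, week 24 for Group B)*. Repeat the condition at the head of section 11, and use one name for step 11 in the opening list and in the body. Record the interview and assessment dates for each participant so that the order can be checked.

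For participants already interviewed, tabulate the order by group before analysis. If any interview came first, report how many.

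The cost is a wording change and a date entry. The interview may fall a few days later, with slightly less fresh recall of the games. Training and outcome measures are unaffected.
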